#### 5. STUDY TIMELINE

Months	-6	-3	0	3	6	9	12	15	18	21	24
Site 1	•	•	x	x	x	-	-	-			
Site 2	•	•	•	x	x	x	-	-	-		
Site 3	•	•	•	•	x	x	x	-	-	-	
Site 4	•	•	•	•	•	x	x	x	-	-	-

• baseline data collection

X mHealth triage tool intervention phase

- follow up phase

#### 6. SAFETY AND ETHICAL ASPECTS OF THE PROJECT

**a) Potential Risks:** The proposed research project poses a minimal risk to subjects who choose to participate, using the NIH definition of “the probability and magnitude of harm or discomfort anticipated in the research are not greater in and of themselves than those ordinarily encountered in daily life or during the performance of routine physical or psychological examinations or tests.”

The potential risks of this study include:

(1) Unintentional disclosure of private health or identifying information. This risk is unlikely to occur. If an information breach were to occur the risk to the subject(s) would likely be minimal, although it is theoretically possible that physical or emotional harm could result from information disclosure.

(2) Physical or psychological distress from participation. Asking patients to recall the context and discuss the consequences of their injury may cause them some psychological stress, but this risk should be minimal.

(3) Time and financial loss while participating in follow-up surveys. Study involvement will require some time lost for survey completion, however the risk to the subject will be minimal as the surveys should not take more than 15 -20 mins to complete.

##### Private Health or Identifying Information:

Mobile phone numbers, names, and addresses will be collected as part of the trauma registry at the ten collaborating hospital sites in Cameroon. Data on patient symptoms and well-being will be collected from all subjects at timepoints post-discharge. Data on subject's physical and economic disability will also be collected during all follow-up timepoints (2 weeks, 1 month, 3 months, and 6 months). No additional individually identifiable private information will be specifically collected for the proposed research project.

##### b) Protections Against Risk

To protect and minimize against the unintentional disclosure of private health or identifying information: Patient data will be recorded on paper forms which will be stored in secure lock boxes at each of the hospital site for up to five years prior to local destruction. Trauma registry research assistants will enter data into the encrypted, password-protected, online database hosted on REDCap. All personnel with the potential to handle patient data (i.e. program manager, study investigators, field supervisors, RAs) will undergo standard protection of human data training and certification.

While the risk for physical and psychological discomfort are low, subjects will be informed that they are free to skip any survey questions that make them feel uncomfortable. To offset any financial risks that research participation will cause,

post-discharge trauma patients will be transferred mobile phone credits after any phone interviews conducted for the study. Subjects will be informed that their responses will be entered into an electronic database, which will be encrypted and password-protected. Subjects will also be informed that the data will be accessible only to research personnel.

It is highly unlikely that adverse effects will result directly from the study interventions. However, it is possible that during follow-up calls, patients may disclose information that suggests immediate need for medical or professional intervention. If subjects are suspected to have urgent medical or safety needs, research assistants will promptly report this information to the Cameroon-based Project Manager and [name] for adjudication. Where necessary, subjects will be re-contacted to urge them to seek medical care.

## **7. TRIALS AND SPONSORS MANAGEMENT**

The trial is sponsored by the National Institute of Health. The Study investigators will oversee the safety of the trial to ensure that the trial is conducted to quality and safety standards.

## **8. ROLES OF INVESTIGATORS AND COLLABORATORS**

The study PIs and co-investigators are responsible for ensuring study fidelity and making changes in study protocol as needed. Project managers and field supervisors are responsible for day to day supervision of data collection by research assistants and informing study investigators of any adverse events. Study PIs core will provide logistic support and oversight to ensure smooth running of study activities.

## **9. DISSEMINATION PLAN**

Results from the study will be presented at conferences, in peer-reviewed journals, and will be discussed with the Cameroon MOPH on an ongoing basis through our team's partnership with the MOPH. Our partnership has regularly presented interim analyses, lessons learned, and final results and recommendations of our research to the MOPH in Cameroon, so we will continue to do this throughout this project on an annual (or more, if needed) basis.

## **10. LIMITATIONS**

The proposed phone-based approach to improve post discharge care will not reach individuals without access to a phone (either their own or in their household); however, given high levels of cell phone penetration in Cameroon which continues to increase, this will represent a small proportion of patients. In addition, patients may be concerned about hospital contact if they perceive it to be related to billing; however, in our prior trauma registry research we developed enhanced patient education protocols to mitigate this possibility. Self-reported outcomes in Aim 3 will be verified with medical record review whenever possible; nevertheless, it may not be feasible for everyone.

The recruitment and retention of study subjects will be monitored by the study PIs on a quarterly basis. Every quarter, the project manager will prepare a written report presenting data—in aggregate and by hospital site—on: patient enrollment, comparison of target to actual enrollment, study subjects' demographics and overall status, and the retention of subjects in the study overtime. Additionally, the Cameroon-based project manager will provide information on any adverse events among study subjects or alert study investigators to subjects whose responses to the mhealth screening tool trigger concern. Following the review of these interim analysis reports, the PIs will (1) recommend any modifications that are required to enhance recruitment and retention of study participants and (2) determine whether it would be necessary to reconsider the study's design.

## ADDENDUM:

A pilot phase was started in July 2019 with actual recruitment for the study commencing in August 2019. Baseline data was collected from August 2019 using the aGOSE survey till February 2020 when the intervention phase commenced at the first site. New patients' recruitment for aGOSE data was stopped in June 2021 with 6-month follow-up completed by December 2022-January 2023.

The study's original research strategy included 3 hospitals. During the time from notice of award to receipt of funding and initiation of study procedures, approximately 14 months elapsed. This delay was in part due to the US PI moving institutions from UCSF to UCLA. During that time, the Cameroon Trauma Registry (CTR) Expanded from 3 hospitals to 4. Correspondingly, the mHealth study was implemented in all four hospitals included in the CTR (as indicated in the final study protocol).

Under the parent award, the intervention (a telephone-based triage tool) and associated follow-up physician exams were designed to be implemented in a stepped-wedge fashion at partner hospital sites, staggered by three months for each facility's start date. This step-wedge study design would have enabled us to compare intervention patients with historical controls, while controlling for temporal trends. However, research delays and interruptions due to the suspension of data collection activities at the peak of the COVID-19 pandemic in 2020 (April – September 2020) led us to discontinue this approach to maximize patient recruitment for the cross-validation of our triage instrument. We abandoned our original step-wedge study design in the revised research plan as it was no longer feasible to implement under the remaining study timeline and would incur unacceptable delays at the potential expense of instrument validation.

Adhering to local and national guidelines in Cameroon, we temporarily suspended all follow-up physician exams of discharged trauma patients to prevent direct contact between patients and research staff, as well as to reduce patient exposure during travel. Consequently, we were forced to delay the implementation of our intervention (telephone-based triage tool) at all sites due to a lack of capacity to cross-validate triage results with physician assessments. Physician exams (Aim 2) had been initiated only one month prior to this suspension at our first partner hospital site in accordance with our step-wedge study design. We resumed all research activities in September 2020, after the Cameroonian Ministry of Public Health had established protocols for COVID-19 control and prevention in the workplace, and our team could reliably supply personal protective equipment for all research staff. Patient recruitment in our intervention cohort was thus delayed for a total period of six months. COVID-19 impacted patient recruitment and we applied for a 12-month funded supplement to enable us to accrue a sample size enough to validate our tool.

*Supplement Sample Size Calculations Adjustment:* Data collected from our prospective cohort will be divided into training and validation groups (70% and 30% of the overall cohort respectively). Our original sample size was calculated to account for a conservative prevalence of 10% of contacted patients needing further follow-up care. Based upon detecting a significant departure from 50% specificity, we estimate that we would require approximately 400 patients who are not recommended for follow-up care to be included in our validation sample. We will therefore target a sample size of 1330 trauma patients in our triage cohort. New multicenter preliminary data, however, suggest that physician exams leading to a recommendation for further care occur for 50% of contacted patients. This is a significant deviation from prior single-institution Cameroon pilot data that estimated 13.7% of contacted trauma patients would need further care. The inclusion of additional hospital sites that receive patients with more severe injuries as well as selection bias are likely contributing to this difference. If our preliminary findings remain consistent, we anticipate only requiring 220 patients not recommended for follow-up care to be included in our validation sample and 730 patients to be targeted in our triage cohort. Using a conservative estimate for our sample size calculation approach enables us to create a buffer and ensure our study is adequately powered to achieve statistical significance.

Triage tool was administered at 2 weeks with physician examination assessments from February 2020 till August 2022 (with the pauses noted above). Final 2 weeks follow-up was completed on September 14, 2022.

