## Primary Outcomes

mHealth triage tool score; physician exam determination for “needs further care” or “does not need further care”.

**Sample Size:** The preliminary triage instrument has 13 variables derived from 7 questions. A minimum sample size of 10 participants per variable per potential model outcome (either needing further care or not needing care) is required to adequately power regression analysis. Our preliminary data suggests that physician exams leading to a recommendation for further care occur for 13.7% of calls. Conservatively estimating that 10% of contacted patients will require further care, a sample size of 1300 patients in the triage cohort will be targeted.

**Data Analysis:** Data from the prospective cohort will be divided into training and validation groups (70% and 30% of the overall cohort respectively). Stepwise multiple regression with bidirectional elimination will be used on the training group dataset to build the best model for predicting physician recommendation for further care (considered as a binary outcome). Survey questions that are found not to contribute significantly to prediction will be dropped from the final triage tool. The resultant model will be applied to data from the validation cohort. To establish predictive accuracy, we will assess calibration of the model by comparing the mean error between the predicted risk and actual physician response in this cohort. Receiver operating characteristic (ROC) curves will be calculated to evaluate the discrimination of the model. As the consequences of a false-positive survey leading to unnecessary patient follow-up are minimal, whereas false-negatives may result in poor health outcomes, risk cutoffs will target a highly sensitive test with minimal false negatives. Ratings of telephone follow-up acceptability will be aggregated and summarized.

**Aim 3: Characterize the impact of timely follow-up on long-term disability and socioeconomic consequences associated with trauma in Cameroon.**

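### Addendum sample size: the targets 1330 and 730 are 400 and 220 divided by the 30% validation share alone, so the labels, totals and prevalences do not agree

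*Combined protocol and SAP*

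**What the plan says.** The Addendum (Supplement Sample Size Calculations Adjustment) splits the cohort 70% training and 30% validation. It recalls that "Our original sample size was calculated to account for a conservative prevalence of 10% of contacted patients needing further follow-up care". It then sizes the validation: "Based upon detecting a significant departure from 50% specificity", the authors estimate that "we would require approximately 400 patients who are not recommended for follow-up care to be included in our validation sample", and conclude: "We will therefore target a sample size of 1330 trauma patients in our triage cohort".

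It next reports that newer multicentre data "suggest that physician exams leading to a recommendation for further care occur for 50% of contacted patients". On condition that this persists, "we anticipate only requiring 220 patients not recommended for follow-up care to be included in our validation sample and 730 patients to be targeted". The paragraph closes: "Using a conservative estimate for our sample size calculation approach enables us to create a buffer and ensure our study is adequately powered". It states no alpha, sidedness, power or alternative specificity.

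The main protocol sizes Aim 2 by a different rule, ten participants per variable per outcome for 13 variables: "Conservatively estimating that 10% of contacted patients will require further care, a sample size of 1300 patients in the triage cohort will be targeted".

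**The concern.** Specificity is estimated only in patients whom the physician judges not to need further care (non-cases below). A requirement expressed in non-cases must be converted into a cohort in two steps: divide by the share of non-cases, then by the 30% validation share. The Addendum's totals appear to skip the first step.

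The direction also looks wrong. When more patients need care, fewer non-cases are available, so a given specificity test needs a larger cohort. The Addendum asks for a smaller one and offers the change in prevalence as its only reason.

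This is the only sizing given for the specificity test, and it ends by asserting adequate power. A reader would credit the validation with more non-cases than the totals can supply, and could take 730 as enough at the prevalence then being seen.

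**Working it through.** **Inputs (all from the Addendum).** Validation share 0.30. Prevalence of needing care 10% or 50%, so the non-case share is 0.90 or 0.50. Stated counts 400 and 220. Stated totals 1330 and 730.

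**1. Reproduce the stated totals.** Total = count / 0.30:
- 400 / 0.30 = 1333, stated as 1330
- 220 / 0.30 = 733, stated as 730

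With the non-case share included, total = count / (0.30 × (1 − prevalence)):
- 400 / (0.30 × 0.90) = 1481
- 220 / (0.30 × 0.50) = 1467

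Only the first formula reproduces the plan. The counts were therefore used as whole validation groups.

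**2. Non-cases that the totals deliver.** Non-cases = total × 0.30 × (1 − prevalence):

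| Cohort | Prevalence | Validation group | Expected non-cases | Stated count |
|---|---|---|---|---|
| 1330 | 10% | 399 | 359 | 400 |
| 1330 | 50% | 399 | 200 (199.5) | 220 |
| 730 | 50% | 219 | 110 (109.5) | 220 |

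**3. Direction.** With the null, alternative, alpha and power fixed, the number of non-cases required does not depend on prevalence. The cohort must then change by 0.90 / 0.50 = 1.80 when prevalence goes from 10% to 50%. The plan goes from 1330 to 730, a fall of 1 − 730/1330 = 45%.

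**4. Possible causes.**
- (a) The labels are right and the (1 − prevalence) step was left out. The totals become about 1481 and 1467. One version of this treats 400 and 220 as the non-case shares of a single validation group of about 440 (400/0.90 = 444; 220/0.50 = 440). That would explain the fall from 400 to 220, but the cohort would be about 1470 to 1480 in both scenarios.
- (b) 400 and 220 are whole validation groups and the two prevalence scenarios were swapped: 400 × 0.50 = 200 and 220 × 0.90 = 198, nearly the same non-case requirement.

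Both patterns rest on one coincidence, 400/220 = 1.82 against 0.90/0.50 = 1.80, so it cannot decide between them. Only (b) also explains the division by 0.30.

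**5. Size of the effect.** The test settings are not stated, so a range is shown. The entries are the specificity p detectable against 50%, from the one-sample normal approximation n = [(z_α × 0.5 + z_power × √(p(1 − p))) / (p − 0.5)]², with an assumed alpha of 5%:

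| Non-cases | One-sided, 80% power | One-sided, 90% | Two-sided, 80% | Two-sided, 90% |
|---|---|---|---|---|
| 359 | 56.5% | 57.7% | 57.4% | 58.5% |
| 200 | 58.7% | 60.2% | 59.8% | 61.3% |
| 110 | 61.7% | 63.7% | 63.2% | 65.2% |

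**The case against.** The strongest reply is that little depends on this paragraph. The kept target is 1330, and 730 is only a conditional remark. The Addendum puts the end of triage calls and examinations in August 2022 and of two-week follow-up in September 2022, so the observed non-cases and the confidence interval for specificity will govern interpretation. Aim 2 Data Analysis also puts sensitivity ahead of specificity. All of this stands, and it limits the stakes.

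Second, with the test settings unstated, the alternative might have differed between scenarios, so that 220 and 400 answer different questions. That is possible, but the text says nothing of it. Even then, 730 at 50% prevalence yields 110 non-cases and not 220.

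Third, the closing sentence on a conservative estimate may refer to the events-per-variable sizing, for which 10% is conservative, or simply to keeping 1330 over 730. The wording allows this. The criticism of that sentence therefore applies only so far as it is read as covering specificity.

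A reader might infer that the two scenarios were certainly swapped. The document does not show this, since cause (a) fits the same ratio and keeps the labels and scenario order. A reader might also infer that the validation is underpowered. That is not shown either: under (b), 1330 at 50% gives 199.5 non-cases against a requirement of about 198 to 200, which just meets it. Under (a), it is about 9% below 220 (20.5/220).

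**Conclusion.** The point holds as an internal inconsistency. Both totals follow from the stated counts only if nobody in the validation group needs care, which contradicts the 10% and 50% assumed in the same paragraph. The shortfall against the stated counts is about 10% for 1330 at 10% prevalence (359 against 400), and half for 730 at 50% (110 against 220). These figures need only the 30% split and the stated prevalences.

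The direction argument rests on one further premise, that the same test is meant in both scenarios. The text gives no reason to think otherwise. The detectable-specificity ranges rest on assumed alpha, sidedness and power.

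The document does not reveal which slip occurred. The main protocol's 1300 is unaffected: 13 × 10 / 0.10 = 1300. This should be corrected for reporting, but it is not evidence that the study needs more patients or that its validation fails.

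**What to change.** In the Addendum's sample size paragraph:

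1. State the alpha, sidedness, power and alternative specificity behind 400 and 220.
2. Say whether 400 and 220 are non-cases or whole validation groups, and at which prevalence each applies. Correct the labels or the totals accordingly.
3. Restate the expected validation non-cases (about 359, 200 and 110) with the power or detectable specificity for each.
4. Do not present 730 as sufficient at 50% prevalence unless the restated figures support it.
5. Confine the closing claim of a conservative buffer and adequate power to the events-per-variable sizing, unless the restated specificity figures also support it. For that sizing, higher prevalence does add margin: 1330 × 0.50 × 0.70 = about 465 training patients needing care, against 13 × 10 = 130.

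The cost is recovering the original calculation, rewording one paragraph and adding a short table. No extra patients are needed. The downside is that the stated sizing for specificity may look less favourable.

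### The addendum names selection bias as a likely contributor to the 50% rate, yet the Aim 2 model and its calibration check stay within the same examined cohort, with no weighted analysis

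*Combined protocol and SAP*

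**What the plan says.** The addendum (Supplement Sample Size Calculations Adjustment) reports new multicentre preliminary data in which "physician exams leading to a recommendation for further care occur for 50% of contacted patients". It contrasts this with "prior single-institution Cameroon pilot data that estimated 13.7% of contacted trauma patients would need further care" and comments: "The inclusion of additional hospital sites that receive patients with more severe injuries as well as selection bias are likely contributing to this difference". The only consequence drawn is for sample size: 1330 is kept as a buffer over the 730 that would suffice if the 50% persists. The same paragraph restates the 70%/30% split of one cohort.

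The Aim 2 Data Analysis text is not changed by this. It says "Stepwise multiple regression with bidirectional elimination will be used on the training group dataset to build the best model for predicting physician recommendation", and then, for the remaining 30%, "we will assess calibration of the model by comparing the mean error between the predicted risk and actual physician response in this cohort". ROC curves follow, with a risk cut-off chosen for high sensitivity. Neither text mentions weights, a comparison of examined with unexamined patients, or a sensitivity analysis for selection. Adjustment for site and injury severity appears only under Aim 3.

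The Aim 2 Implementation section describes who enters the cohort: patients contacted at two weeks, who give an additional consent, answer the triage questions and then attend an exam. The exam is offered whatever the triage result. The Aim 1 approach lists what is extracted from the registry: demographics, clinical course, injury severity, disposition and phone number.

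**The concern.** A bias that the sponsor considers likely has no counterpart in the analysis it could affect. A held-out 30% carries whatever selection shaped the whole cohort, so agreement there says nothing about contacted patients who declined or did not attend. The candidate predictors are 13 variables from the phone questions. Site, mechanism and injury severity are not among them, so selection on those factors is not conditioned on in the model and can distort its absolute risks.

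The cut-off is exposed by a second route. Patients whose answers raise concern are told to return to care, while the others are only asked to schedule an exam. If the first group attends more often, too few false negatives are observed and the tool looks more sensitive than it is. The plan treats false negatives as the costly error, so this is the quantity it most needs to get right.

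**Working it through.** **The plan's own figures.** 13 variables × 10 / 0.10 = 1300, as stated. 400 / 0.30 = 1333 against the stated 1330, and 220 / 0.30 = 733 against 730. These are the only calculations in which the prevalence, and its change, is used.

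**Why the planned check cannot reveal shared selection.** The documents do not say how the split is made; take it as random. A logistic model with an intercept reproduces the training prevalence on average. If that is 50%, the expected prevalence in the 30% is also 50%, so the expected mean error is about 0.50 − 0.50 = 0. This holds whatever the prevalence p among all contacted patients.

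**Outcome-dependent selection: a range, because the share due to selection is not given.** If entry to the cohort depends only on the outcome, the intercept is shifted by logit(0.50) − logit(p), and a predicted risk r corresponds to a true risk with logit equal to logit(r) minus that shift.

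| Assumed p | Shift (logits) | Predicted 20% means | Predicted 50% means |
|---|---|---|---|
| 13.7% | 1.84 | 3.8% | 13.7% |
| 20% | 1.39 | 5.9% | 20% |
| 30% | 0.85 | 9.7% | 30% |
| 40% | 0.41 | 14.3% | 40% |
| 50% (no selection) | 0 | 20% | 50% |

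The first row requires patients needing care to be (0.50/0.50) / (0.137/0.863) = 6.3 times as likely to enter the cohort as the others. Under this mechanism, sensitivity and specificity at a fixed score do not change.

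**Attendance that depends on the tool result.** Let v1 and v0 be the proportions of tool-positive and tool-negative patients examined.

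- Observed sensitivity = Se·v1 / [Se·v1 + (1 − Se)·v0]
- Observed specificity = Sp·v0 / [Sp·v0 + (1 − Sp)·v1]

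Assume true Se = 0.80 and Sp = 0.60.

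- v1 = 0.80, v0 = 0.40: sensitivity 0.64 / (0.64 + 0.08) = 0.89; specificity 0.24 / (0.24 + 0.32) = 0.43.
- v1 = 0.60, v0 = 0.20: sensitivity 0.48 / (0.48 + 0.04) = 0.92; specificity 0.12 / (0.12 + 0.24) = 0.33.

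With a true prevalence of 13.7%, the observed prevalence in these two cases would be only 17.0% and 18.7%. This mechanism can therefore distort sensitivity noticeably while explaining little of the rise to 50%.

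**The case against.** A reader might infer that the sponsor concedes the cohort is selected towards patients who need care, and that the risks are therefore too high by 1.84 logits. The documents do not support this. The addendum names selection bias as one contributor to a difference between two data sets, after naming more severe injuries at added sites. It does not say which data set is selected or in which direction; part of the bias could lie in the single-institution pilot. A more severe case mix is not bias. The 50% is itself preliminary.

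A reader might also infer that the cut-off is bound to be wrong. It is not: under the mechanism that gives 1.84, sensitivity and specificity at a given score hold. Only attendance linked to symptoms or triage answers disturbs them. Nor does over-predicted risk run against the plan's priorities, since the plan regards false positives as cheap. Predictive values would move with prevalence, but they are not a planned output.

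There are real safeguards: the exam is offered regardless of triage result, at hospital or at home, with travel compensation, and there are repeated call attempts and phone credit. They reduce selection but do not measure what remains.

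The strongest objection concerns the remedy. Weights from baseline registry data do not correct selection on the outcome itself, and how a patient feels at two weeks is not in the registry. That is a reason to add the triage answers to the weights for examination, and not to insist on a weighted intercept in the released tool. It is also fair that people never reached cannot be served by a phone tool, so the target should be contacted patients.

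What stands is that the planned check cannot show whether results in examined patients carry over to contacted patients, and data that would partly show it are already held.

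**Conclusion.** The concern holds in a limited form. The plan names a likely selection bias and then fits and checks the model within the one examined cohort; that the analysis is unweighted is inferred from the absence of any mention of weights. Near-zero mean error in the 30% would support calibration among examined patients, not among all contacted discharged patients. Sensitivity, and hence the cut-off, may be overstated if attendance follows symptoms or triage answers.

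The size cannot be derived from the documents. The intercept error ranges from 0 (no selection) to 1.84 logits (the whole gap from 13.7% to 50% due to outcome-dependent selection), and the upper end sets aside the case-mix cause that the addendum names first. The apparent sensitivity of 0.89 for a true 0.80 rests on assumed attendance. This is a cheap improvement, not a defect that invalidates Aim 2.

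**What to change.** Add to the Aim 2 analysis, specified before the weighted results are seen, an inverse-probability-weighted analysis reported beside the unweighted one:

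- **Contacted to consented and triaged:** weights from registry variables (site, age, gender, mechanism, injury severity, clinical course, disposition).
- **Triaged to examined:** weights from the same variables plus the triage answers.
- **Apply to:** prevalence, calibration, and sensitivity and specificity at the chosen cut-off.
- **Report:** the flow from eligible to contacted, consented and examined, with registry characteristics at each step.
- **Wording:** if weighted and unweighted results differ, describe the 30% check as internal calibration in examined patients only.

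The weighted intercept need not be used in the released tool.

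The cost is SAP text and analysis time, with no new patients or visits. Precision falls: 30% of 1330 is 399 validation patients, and with an assumed coefficient of variation of the weights of 0.5 to 1, they act as 399 / 1.25 = 319 to 399 / 2 = 200. The documents do not state how complete the registry variables are. Selection on unmeasured factors remains, and the report should say so.
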